12.4. Appendix 4: PML Algorithm

12.5. Appendix 5: Neurological Symptoms Questionnaire

	YES	NO
CCI - This section contained Clinical Outcome Assessment data collection questionnaires or indices, which are protected by third party copyright laws and therefore have been excluded.		

If any of the above are answered “Yes” at any visit, the investigator will contact the medical monitor.

Any neurological symptom that cannot be attributed to a concurrent medical condition or concomitant medication must be referred to a neurologist.

12.6. Appendix 6: Genetic Research

Genetic Research Objectives and Analyses

The objectives of the genetic research are to investigate the relationship between genetic variants and:

- Response to medicine, including belimumab, ritixumab or any concomitant medicines;
- Sjögren's syndrome susceptibility, severity, and progression and related conditions

Genetic data may be generated while the study is underway or following completion of the study. Genetic evaluations may include focused candidate gene approaches and/or examination of a large number of genetic variants throughout the genome (whole genome analyses). Genetic analyses will utilize data collected in the study and will be limited to understanding the objectives highlighted above. Analyses may be performed using data from multiple clinical studies to investigate these research objectives.

Appropriate descriptive and/or statistical analysis methods will be used. A detailed description of any planned analyses will be documented in a Reporting and Analysis Plan (RAP) prior to initiation of the analysis. Planned analyses and results of genetic investigations will be reported either as part of the clinical RAP and study report, or in a separate genetics RAP and report, as appropriate.

Study Population

Any subject who is enrolled in the study can participate in genetic research. Any subject who has received an allogeneic bone marrow transplant must be excluded from the genetic research.

Study Assessments and Procedures

A key component of successful genetic research is the collection of samples during clinical studies. Collection of samples, even when no *a priori* hypothesis has been identified, may enable future genetic analyses to be conducted to help understand variability in disease and medicine response.

- A 6 mL blood sample will be taken for Deoxyribonucleic acid (DNA) extraction. A blood sample is collected at the baseline visit, after the subject has been randomized and provided informed consent for genetic research. Instructions for collection and shipping of the genetic sample are described in the laboratory manual. The DNA from the blood sample may undergo quality control analyses to confirm the integrity of the sample. If there are concerns regarding the quality of the sample, then the sample may be destroyed. The blood sample is taken on a single occasion unless a duplicate sample is required due to an inability to utilize the original sample.

The genetic sample is labeled (or "coded") with the same study specific number used to label other samples and data in the study. This number can be traced or linked back to the

subject by the investigator or site staff. Coded samples do not carry personal identifiers (such as name or social security number).

Samples will be stored securely and may be kept for up to 15 years after the last subject completes the study, or GSK may destroy the samples sooner. GSK or those working with GSK (for example, other researchers) will only use samples collected from the study for the purpose stated in this protocol and in the informed consent form. Samples may be used as part of the development of a companion diagnostic to support the GSK medicinal product.

Subjects can request their sample to be destroyed at any time.

Informed Consent

Subjects who do not wish to participate in the genetic research may still participate in the study. Genetic informed consent must be obtained prior to any blood being taken.

Subject Withdrawal from Study

If a subject who has consented to participate in genetic research withdraws from the clinical study for any reason other than being lost to follow-up, the subject will be given a choice of one of the following options concerning the genetic sample, if already collected:

- Continue to participate in the genetic research in which case the genetic DNA sample is retained
- Discontinue participation in the genetic research and destroy the genetic DNA sample

If a subject withdraws consent for genetic research or requests sample destruction for any reason, the investigator must complete the appropriate documentation to request sample destruction within the timeframe specified by GSK and maintain the documentation in the site study records.

Genotype data may be generated during the study or after completion of the study and may be analyzed during the study or stored for future analysis.

- If a subject withdraws consent for genetic research and genotype data has not been analyzed, it will not be analyzed or used for future research.
- Genetic data that has been analyzed at the time of withdrawn consent will continue to be stored and used, as appropriate.

Screen and Baseline Failures

If a sample for genetic research has been collected and it is determined that the subject does not meet the entry criteria for participation in the study, then the investigator should instruct the subject that their genetic sample will be destroyed. No forms are required to complete this process as it will be completed as part of the consent and sample reconciliation process. In this instance, a sample destruction form will not be available to include in the site files.

Provision of Study Results and Confidentiality of Subject's Genetic Data

GSK may summarize the genetic research results in the clinical study report, or separately and may publish the results in scientific journals.

GSK may share genetic research data with other scientists to further scientific understanding in alignment with the informed consent. GSK does not inform the subject, family members, insurers, or employers of individual genotyping results that are not known to be relevant to the subject's medical care at the time of the study, unless required by law. This is due to the fact that the information generated from genetic studies is generally preliminary in nature, and therefore the significance and scientific validity of the results are undetermined. Further, data generated in a research laboratory may not meet regulatory requirements for inclusion in clinical care.

12.7. Appendix 7: Definition of and Procedures for Recording, Evaluating, Follow-Up and Reporting of Adverse Events

12.7.1. Definition of Adverse Events

Adverse Event Definition:

- An AE is any untoward medical occurrence in a patient or clinical investigation subject, temporally associated with the use of a medicinal product, whether or not considered related to the medicinal product.
- NOTE: An AE can therefore be any unfavorable and unintended sign (including an abnormal laboratory finding), symptom, or disease (new or exacerbated) temporally associated with the use of a medicinal product.

Events meeting AE definition include:

- Any abnormal laboratory test results (hematology, clinical chemistry, or urinalysis) or other safety assessments (e.g., ECGs, radiological scans, vital signs measurements), including those that worsen from baseline, and felt to be clinically significant in the medical and scientific judgement of the investigator.
- Exacerbation of a chronic or intermittent pre-existing condition including either an increase in frequency and/or intensity of the condition.
- New conditions detected or diagnosed after study treatment administration even though it may have been present prior to the start of the study.
- Signs, symptoms, or the clinical sequelae of a suspected interaction.
- Signs, symptoms, or the clinical sequelae of a suspected overdose of either study treatment or a concomitant medication (overdose per se will not be reported as an AE/SAE unless this is an intentional overdose taken with possible suicidal/self-harming intent. This should be reported regardless of sequelae).
- "Lack of efficacy" or "failure of expected pharmacological action" per se will not be reported as an AE or SAE. However, the signs and symptoms and/or clinical sequelae resulting from lack of efficacy will be reported if they fulfil the definition of an AE or SAE.

Events NOT meeting definition of an AE include:

- Any clinically significant abnormal laboratory findings or other abnormal safety assessments which are associated with the underlying disease, unless judged by the investigator to be more severe than expected for the subject's condition.
- The disease/disorder being studied or expected progression, signs, or symptoms of

the disease/disorder being studied, unless more severe than expected for the subject's condition.
• Medical or surgical procedure (e.g., endoscopy, appendectomy): the condition that leads to the procedure is an AE.
• Situations where an untoward medical occurrence did not occur (social and/or convenience admission to a hospital).
• Anticipated day-to-day fluctuations of pre-existing disease(s) or condition(s) present or detected at the start of the study that do not worsen.

12.7.2. Definition of Serious Adverse Events

If an event is not an AE per definition above, then it cannot be an SAE even if serious conditions are met (e.g., hospitalization for signs/symptoms of the disease under study, death due to progression of disease, etc).

Serious Adverse Event (SAE) is defined as any untoward medical occurrence that, at any dose:

a. Results in death

b. Is life-threatening

NOTE:

The term 'life-threatening' in the definition of 'serious' refers to an event in which the subject was at risk of death at the time of the event. It does not refer to an event, which hypothetically might have caused death, if it were more severe.

c. Requires hospitalization or prolongation of existing hospitalization

NOTE:

- In general, hospitalization signifies that the subject has been detained (usually involving at least an overnight stay) at the hospital or emergency ward for observation and/or treatment that would not have been appropriate in the physician's office or out-patient setting. Complications that occur during hospitalization are AEs. If a complication prolongs hospitalization or fulfills any other serious criteria, the event is serious. When in doubt as to whether "hospitalization" occurred or was necessary, the AE should be considered serious.
- Hospitalization for elective treatment of a pre-existing condition that did not worsen from baseline is not considered an AE.

d. Results in disability/incapacity

NOTE:

- The term disability means a substantial disruption of a person's ability to conduct normal life functions.

- This definition is not intended to include experiences of relatively minor medical significance such as uncomplicated headache, nausea, vomiting, diarrhea, influenza, and accidental trauma (e.g. sprained ankle) which may interfere or prevent everyday life functions but do not constitute a substantial disruption

e. Is a congenital anomaly/birth defect

f. Other situations:

- Medical or scientific judgment should be exercised in deciding whether reporting is appropriate in other situations, such as important medical events that may not be immediately life-threatening or result in death or hospitalization but may jeopardize the subject or may require medical or surgical intervention to prevent one of the other outcomes listed in the above definition. These should also be considered serious.
- Examples of such events are invasive or malignant cancers, intensive treatment in an emergency room or at home for allergic bronchospasm, blood dyscrasias or convulsions that do not result in hospitalization, or development of drug dependency or drug abuse

g. Is associated with liver injury and impaired liver function defined as:

- ALT \geq 3xULN and total bilirubin* \geq 2xULN (>35% direct), **or**
- ALT \geq 3xULN and INR ** $>$ 1.5.

* Serum bilirubin fractionation should be performed if testing is available; if unavailable, measure urinary bilirubin via dipstick. If fractionation is unavailable and ALT \geq 3xULN and total bilirubin \geq 2xULN, then the event is still to be reported as an SAE.

** INR testing not required per protocol and the threshold value does not apply to subjects receiving anticoagulants. If INR measurement is obtained, the value is to be recorded on the SAE form.

12.7.3. Definition of Cardiovascular Events

Cardiovascular Events (CV) Definition:

Investigators will be required to fill out the specific CV event page of the CRF for the following AEs and SAEs:

- Myocardial infarction/unstable angina
- Congestive heart failure
- Arrhythmias
- Valvulopathy
- Pulmonary hypertension
- Cerebrovascular events/stroke and transient ischemic attack

- Peripheral arterial thromboembolism
- Deep venous thrombosis/pulmonary embolism
- Revascularization

12.7.4. Recording of AEs and SAEs

AEs and SAE Recording:

- When an AE/SAE occurs, it is the responsibility of the investigator to review all documentation (e.g., hospital progress notes, laboratory, and diagnostics reports) relative to the event.
- The investigator will then record all relevant information regarding an AE/SAE in the CRF
- It is **not** acceptable for the investigator to send photocopies of the subject's medical records to GSK in lieu of completion of the GSK AE/SAE CRF page.
- There may be instances when copies of medical records for certain cases are requested by GSK. In this instance, all subject identifiers, with the exception of the subject number, will be blinded on the copies of the medical records prior to submission to GSK.
- The investigator will attempt to establish a diagnosis of the event based on signs, symptoms, and/or other clinical information. In such cases, the diagnosis will be documented as the AE/SAE and not the individual signs/symptoms.
- Subject-completed patient reported outcome questionnaires and the collection of AE data are independent components of the study.
- Responses to each question in the patient reported outcome questionnaires will be treated in accordance with standard scoring and statistical procedures detailed by the scale's developer.
- The use of a single question from a multidimensional health survey to designate a cause-effect relationship to an AE is inappropriate.

12.7.5. Evaluating AEs and SAEs

Assessment of Intensity

The investigator will make an assessment of intensity for each AE and SAE reported during the study and will assign it to one of the following categories:

- Mild: An event that is easily tolerated by the subject, causing minimal discomfort and not interfering with everyday activities.
- Moderate: An event that is sufficiently discomforting to interfere with normal everyday activities

- Severe: An event that prevents normal everyday activities. - an AE that is assessed as severe will not be confused with an SAE. Severity is a category utilized for rating the intensity of an event; and both AEs and SAEs can be assessed as severe.
- An event is defined as 'serious' when it meets at least one of the pre-defined outcomes as described in the definition of an SAE.

Assessment of Causality

- The investigator is obligated to assess the relationship between study treatment and the occurrence of each AE/SAE.
- A "reasonable possibility" is meant to convey that there are facts/evidence or arguments to suggest a causal relationship, rather than a relationship cannot be ruled out.
- The investigator will use clinical judgment to determine the relationship.
- Alternative causes, such as natural history of the underlying diseases, concomitant therapy, other risk factors, and the temporal relationship of the event to the study treatment will be considered and investigated.
- The investigator will also consult the Investigator Brochure (IB) and/or Product Information, for marketed products, in the determination of his/her assessment.
- For each AE/SAE the investigator **must** document in the medical notes that he/she has reviewed the AE/SAE and has provided an assessment of causality.
- There may be situations when an SAE has occurred and the investigator has minimal information to include in the initial report to GSK. However, **it is very important that the investigator always make an assessment of causality for every event prior to the initial transmission of the SAE data to GSK.**
- The investigator may change his/her opinion of causality in light of follow-up information, amending the SAE data collection tool accordingly.
- The causality assessment is one of the criteria used when determining regulatory reporting requirements.

Follow-up of AEs and SAEs

- The investigator is obligated to perform or arrange for the conduct of supplemental measurements and/or evaluations as may be indicated or as requested by GSK to elucidate as fully as possible the nature and/or causality of the AE or SAE.
- The investigator is obligated to assist. This may include additional laboratory tests or investigations, histopathological examinations or consultation with other health care professionals.
- If a subject dies during participation in the study or during a recognized follow-up period, the investigator will provide GSK with a copy of any post-mortem findings, including histopathology.
- New or updated information will be recorded in the originally completed CRF.
- The investigator will submit any updated SAE data to GSK within the designated reporting time frames.

12.7.6. Reporting of SAEs to GSK**SAE reporting to GSK via InForm**

- Primary mechanism for reporting SAEs to GSK will be the electronic data collection tool.
- If the electronic system is unavailable for greater than 24 hours, the site will use the paper SAE data collection tool and fax it to the Medical Monitor or designee.
- Site will enter the serious adverse event data into the electronic system as soon as it becomes available.
- After the study is completed at a given site, the electronic data collection tool (e.g., InForm system) will be taken off-line to prevent the entry of new data or changes to existing data.
- If a site receives a report of a new SAE from a study subject or receives updated data on a previously reported SAE after the electronic data collection tool has been taken off-line, the site can report this information on a paper SAE form or to the Medical Monitor or designee by telephone.
- Contacts for SAE receipt can be found at the beginning of this protocol on the Sponsor/Medical Monitor Contact Information page.

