7.4.1.1. Time Period and Frequency for Collecting AE and SAE Information

- AEs and SAEs will be collected from the start of Study Treatment through the general follow-up period (see Section 4.3 and the Time and Events Table in Section 7.1)
- Medical occurrences that begin prior to the start of study treatment but after obtaining informed consent may be recorded on the Medical History/Current Medical Conditions section of the eCRF.
- Any SAEs assessed as related to study participation (e.g., protocol-mandated procedures, invasive tests, or change in existing therapy) or related to a GSK product will be recorded from the time a subject consents to participate in the study up to and including any follow-up contact.
- During the individualized safety follow-up phase (if applicable, see Section 4.3 and the Time and Events Table in Section 7.1), only SAEs assessed as related to the investigational product or to study participation, fatal SAEs, and designated AESIs (i.e., infections, malignancies, and depression/suicidality/self-injury) will be collected.
- All SAEs will be recorded and reported to GSK within 24 hours, as indicated in [Appendix 7](#).
- Investigators are not obligated to actively seek AEs or SAEs in former study subjects. However, if the investigator learns of any SAE, including a death, at any time after a subject has been discharged from the study, and he/she considers the event reasonably related to the study treatment or study participation, the investigator must promptly notify GSK.

NOTE: The method of recording, evaluating and assessing causality of AEs and SAEs plus procedures for completing and transmitting SAE reports to GSK are provided in [Appendix 7](#).

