12.2. Appendix 2: Liver Safety Required Actions and Follow up Assessments

Phase II liver chemistry stopping and increased monitoring criteria have been designed to assure subject safety and evaluate liver event etiology (in alignment with the FDA premarketing clinical liver safety guidance).
<http://www.fda.gov/downloads/Drugs/GuidanceComplianceRegulatoryInformation/Guidances/UCM174090.pdf>.

Phase II liver chemistry stopping criteria and required follow up assessments

Liver Chemistry Stopping Criteria – Liver Stopping Event	
ALT-absolute	ALT \geq 5xULN
ALT Increase	ALT \geq 3xULN persists for \geq 4 weeks
Bilirubin1, 2	ALT \geq 3xULN and bilirubin \geq 2xULN (>35% direct bilirubin)
INR2	ALT \geq 3xULN and INR>1.5, if INR measured
Cannot Monitor	ALT \geq 3xULN and cannot be monitored weekly for 4 weeks
Symptomatic3	ALT \geq 3xULN associated with symptoms (new or worsening) believed to be related to liver injury or hypersensitivity

Required Actions and Follow up Assessments following ANY Liver Stopping Event

Actions	Follow Up Assessments

 • Immediately discontinue study treatment • Report the event to GSK within 24 hours • Complete the liver event CRF and complete an SAE data collection tool if the event also meets the criteria for an SAE² • Perform liver event follow up assessments • Monitor the subject until liver chemistries resolve, stabilize, or return to within baseline (see MONITORING below) • Do not restart/rechallenge subject with study treatment unless allowed per protocol and GSK Medical Governance approval is granted (refer to Appendix 3) • If restart/rechallenge not allowed per protocol or not granted, permanently discontinue study 	
 • Viral hepatitis serology⁴ • Blood sample for pharmacokinetic (PK) analysis, obtained 6 weeks after last dose⁵ • Serum creatine phosphokinase (CPK) and lactate dehydrogenase (LDH). • Fractionate bilirubin, if total bilirubin \geq 2xULN • Obtain complete blood count with differential to assess eosinophilia • Record the appearance or worsening of clinical symptoms of liver injury, or hypersensitivity, on the AE report form • Record use of concomitant medications on the concomitant medications report

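### Appendix 7 triggers the paper back-up for SAE reports at an outage of more than 24 hours, so a site that follows it can miss the protocol's own 24-hour SAE reporting limit

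*Protocol*

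**What the plan says.** Section 7.4.1.1 sets the limit: "All SAEs will be recorded and reported to GSK within 24 hours". It makes no exception for system outages, does not say when the 24 hours start, and refers the site to Appendix 7 for the procedure.

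Section 12.7.6, in Appendix 7, gives the procedure:

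- Main route: "Primary mechanism for reporting SAEs to GSK will be the electronic data collection tool".
- Back-up: "If the electronic system is unavailable for greater than 24 hours, the site will use the paper SAE data collection tool". The form is faxed to the Medical Monitor or designee.
- After the outage: "Site will enter the serious adverse event data into the electronic system as soon as it becomes available".
- After the site has completed the study and the tool has been switched off: "the site can report this information on a paper SAE form or to the Medical Monitor or designee by telephone". This bullet concerns site close-out, not an outage.

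Section 12.7.5 says of follow-up information: "The investigator will submit any updated SAE data to GSK within the designated reporting time frames". It does not say what those time frames are. Appendix 7 does not repeat the 24-hour limit. The only period of 24 hours in its reporting instructions is the outage threshold.

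Appendix 2 has a parallel limit for liver stopping events ("Report the event to GSK within 24 hours") and asks for the SAE form where the event also qualifies as an SAE.

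**The concern.** A back-up route exists so that a deadline can still be met when the main route fails. Here the outage must exceed 24 hours before the back-up is called for, and the deadline is itself 24 hours. If the system goes down at or after the moment the site learns of the SAE, the stated trigger cannot be reached before the deadline has passed. For an outage of 24 hours or less no alternative is named at all. A site working from Appendix 7, where 7.4.1.1 sends it, could take the outage threshold as permission to wait.

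What is at stake is how soon the sponsor hears of an SAE. Section 7.4.1.6 treats prompt notification of treatment-related SAEs as essential to the sponsor's legal and ethical duties. Section 4.7 says that there are no clinical trial data on giving the two agents together, and relies on close safety monitoring for that reason.

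**Working it through.** The protocol gives no figure to reproduce. The check is a comparison of two timing rules.

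**Inputs**

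- Reporting limit: 24 h (section 7.4.1.1).
- Trigger for paper: system unavailable for more than 24 h (section 12.7.6).
- Start of the reporting clock: awareness of the SAE, t = 0. This is an assumption.
- Outage start: t = s hours. A negative s means that the outage began before awareness.
- Outage duration: d hours.
- The report has not been sent before the outage starts.

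**Formulas**

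- The system returns at t = s + d.
- Paper is triggered only if d > 24, and then only after t = s + 24.
- The limit is t = 24.

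**Outage starts at or after awareness (s ≥ 0).** Here s + 24 ≥ 24, so the paper trigger always falls beyond the limit. Whether the limit is met then depends on the system returning in time, that is on s + d ≤ 24.

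| s (h) | d (h) | System back at (h) | Paper triggered after (h) | 24 h limit by the stated routes |
|---|---|---|---|---|
| 0 | > 24 | after 24 | 0 + 24 = 24 | missed |
| 6 | > 24 | after 30 | 6 + 24 = 30 | missed |
| 4 | 23 | 4 + 23 = 27 | never (23 < 24) | missed |
| 4 | 10 | 4 + 10 = 14 | never | can be met electronically |

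The third row shows that an outage need not exceed 24 hours to cause a late report.

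**Outage starts before awareness (s < 0).** Here s + 24 < 24. With s = −10, a long outage triggers paper just after −10 + 24 = 14 h, which leaves about 24 − 14 = 10 h. An outage with s = −10 that lasts 24 hours or less ends by 14 h at the latest, so electronic entry is possible in time. The same argument holds for any negative s, although the margin shrinks as s approaches 0. With s = −2, paper is triggered just after 22 h, which leaves about 2 h.

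**Result.** The two rules agree when the outage precedes awareness or ends soon enough. They come apart when the outage starts at or after awareness, before the report is sent, and runs past hour 24.

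**The case against.** The strongest reply is that 12.7.6 makes paper mandatory after 24 hours but does not forbid it sooner. Section 7.4.1.1 covers every SAE without exception, so a site that faxes the form at hour 5 meets the limit and breaks nothing in Appendix 7. The bullet might also be read as referring to an outage expected to exceed 24 hours. Section 7.4.7 sends sites to the study reference manual for detailed guidance on transmitting SAE reports for serious infections, malignancy, death and signs of PML, and that manual is not at hand. It may deal with outages.

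Much of this stands. It rules out several stronger readings that a reader might infer:

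- *That the two rules are incompatible.* They are not. Earlier use of paper is permitted by silence, and some outages satisfy both rules as written.
- *That reports could arrive up to 48 hours after awareness.* That figure comes from counting 24 hours from a site's first failed entry attempt, made as late as hour 24. The bullet refers to how long the system is unavailable, not to time since an attempt. A site that first tries at hour 24 has also used up its allowance by itself.
- *That the primary endpoint is affected.* The endpoint includes SAE incidence. A late report is still a report, and 12.7.6 requires electronic entry once the system is back.
- *That the stopping rule in 5.4.4 is weakened.* Its low-IgG limb already waits for a repeat test about a week later, and the safety review committee meets on a regular cycle. The fatal-infection limb needs no repeat test, but nothing in the protocol shows that a delay of this kind would change a decision.
- *That Appendix 2 widens the problem to all liver stopping events.* It asks for the SAE form only when the event is also an SAE, and does not say that other liver reports follow 12.7.6.

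The reply does not remove the central point. The protocol names one outage route and ties it to a threshold no shorter than the deadline. A site should not have to infer from silence that it may act sooner.

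**Conclusion.** The point holds as a conditional conflict in the current protocol text. A site that follows the 12.7.6 trigger as written can miss the 24-hour limit of 7.4.1.1. The size is a matter of timing. For an outage starting s ≥ 0 hours after awareness, the paper route comes into play only after s + 24 hours, and outages of 24 hours or less may also overrun the limit without bringing it in.

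This rests on two assumptions: that the clock runs from awareness, and that the SAE had not been reported before the outage began. If the clock ran from onset of the event, the time left after awareness would be shorter and the conflict worse. The protocol gives no frequency of outages, so how often this would happen cannot be estimated.

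The consequence is possible late notification of the sponsor. Sample size, alpha and power are untouched. The correction is worth making because it is cheap and concerns safety reporting.

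**What to change.** Tie the back-up to the deadline instead of to the length of the outage. The bullet in 12.7.6 could read:

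> If the electronic system is unavailable when an SAE is to be reported, the site uses the paper SAE tool, or telephone followed by paper, in time to meet the 24-hour limit of section 7.4.1.1, and enters the data electronically once the system is back.

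Adding to the same bullet when the 24 hours start would remove the assumption made above. If the study reference manual repeats the present threshold, it needs the matching change.

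The cost is one or two sentences in Appendix 7. The downside is a few more paper forms to reconcile with the electronic record after short outages.
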